**Prior/Concomitant Therapy**

6. Receiving chemotherapy or immune modulatory drugs (e.g., intravenous [IV] immunoglobulin, cyclosporine) other than anti-retroviral chemotherapy or chronic use of oral or intravenous (IV) corticosteroids (>14 days) within the last 3 months. Brief courses of prednisone/methylprednisolone (<14 days) for treatment of disorders such as synovitis, asthma, etc. are allowed at the discretion of the treating physician
7. Requiring any pre-medication to tolerate FVIII infusions (e.g., antihistamines).

**Prior/Concurrent Clinical Study Experience**

8. Currently participating in another investigational drug study, or having previously participated in a clinical study involving an investigational drug within 30 days of signing informed consent or participated in completed interventional clinical studies with BAY 81-8973 (KOVALTRY).

**Other Exclusions**

9. Unwilling to comply with study visits or other protocol requirements or is not suitable for participation in this study for any reason, according to the Investigator.
10. Planned major surgery, defined as surgery with respiratory assistance and/or general anesthesia.
11. Close affiliation with the investigational site; e.g., a close relative of the investigator, dependent person (e.g., employee or student of the investigational site).

**5.2.2 Part B (PUPs/MTPs) Exclusion Criteria**

Participants are excluded from Part B of the study if any of the following criteria apply:

**Medical Conditions**

1. Any other bleeding disorder that is different from hemophilia A (e.g., von Willebrand disease, hemophilia B).
2. Platelet count  $<100\,000/\text{mm}^3$  based on screening laboratory assessments.
3. Impaired renal function (serum creatinine  $>2\times$  upper limit of normal [ULN]) or active liver disease (alanine aminotransferase [ALT] or aspartate aminotransferase [AST]  $>5\times$  ULN) based on screening laboratory assessments.
4. MTPs with history of FVIII inhibitor formation.
5. Known hypersensitivity to the active substance, mouse or hamster protein.
6. First treatment with KOVALTRY for high-risk bleeding situations (e.g., surgery, intracranial bleed) or requiring intensive or prolonged treatment.
7. Planned major surgery, defined as surgery with respiratory assistance and/or general anesthesia.

**Prior/Concomitant Therapy**

8. Receiving chemotherapy or immune modulatory drugs (e.g., IV immunoglobulin, cyclosporine) other than anti-retroviral chemotherapy or chronic use ( $>14$  days) of oral or IV corticosteroids within the last 3 months. Brief courses ( $<14$  days) of prednisone/methylprednisolone for treatment of disorders such as synovitis, asthma, etc. are allowed at the discretion of the treating physician.
9. Requiring any pre-medication to tolerate FVIII infusions (e.g., antihistamines).

**Prior/Concurrent Clinical Study Experience**

10. Currently participating, or have participated within 30 days of signing informed consent, in another clinical study involving an investigational drug.

**Other Exclusions**

11. Unwilling to comply with study visits or other protocol requirements or is not suitable for participation in this study for any reason, according to the investigator's judgment.
12. Close affiliation with the investigational site (e.g., a close relative of the investigator, dependent person [e.g., employee or student of the investigational site]).
13. Unable to tolerate volume of blood draws required for study participation (see Section 10.2).

### **5.3 Lifestyle Considerations**

No restrictions are required.

#### **5.3.1 Meals and Dietary Restrictions**

No restrictions are required.

#### **5.3.2 Caffeine, Alcohol, and Tobacco**

No restrictions are required.

#### **5.3.3 Concomitant Medications**

Medications that cause a bleeding diathesis (for example, Aspirin® or any acetylsalicylic acid) should be avoided in individuals with hemophilia, except as specifically prescribed by a treating physician. Low dose aspirin should not be discontinued in participants who have been identified to be at risk for cardiovascular events. Further details are provided in Section [6.5](#).

### **5.4 Screen Failures**

Screen failures are defined as participants who consent to participate in the clinical study but are not subsequently receiving study intervention. A minimal set of screen failure information is required to ensure transparent reporting of screen failure participants to meet the Consolidated Standards of Reporting Trials (CONSORT) publishing requirements and to respond to queries from regulatory authorities. Minimal information includes demography, screen failure details, eligibility criteria, and any serious adverse events (AEs).

Individuals who do not meet the criteria for participation in this study (screen failure) cannot be rescreened.

## 6. Study Intervention

Study intervention is defined as any investigational intervention(s), marketed product(s), placebo, or medical device(s) intended to be administered to a study participant according to the study protocol.

### 6.1 Study Intervention Administered

All treatment decisions for identifying appropriate prophylactic treatment regimen should be guided by clinical judgment based on the approved prescribing information (PI) and the individual participant characteristics and treatment response.

**Table 6-1: Study Intervention by Arm and Dose**

Arm Name	Part A		Part B
	Child (Age <12 years)	Adolescent/Adult (Ages ≥12 to 65 years)	
Intervention Name	KOVALTRY	KOVALTRY	KOVALTRY
Type	Full-length human recombinant Factor VIII (rFVIII) protein	Full-length human recombinant Factor VIII (rFVIII) protein	Full-length human recombinant Factor VIII (rFVIII) protein
Dose Formulation	Powder for solution for infusion or infusion	Powder for solution for infusion or infusion	Powder for solution for infusion or infusion
Unit Dose Strengths	250 IU, 500 IU, 1000 IU	250 IU, 500 IU, 1000 IU	250 IU, 500 IU, 1000 IU
Dosage (for prophylaxis)	25 to 50 IU of KOVALTRY per kg body weight (rounded to the nearest vial size) twice weekly, three times weekly, or every other day according to individual requirements for 6 months	12 year-old: 25 to 50 IU of KOVALTRY per kg body weight (rounded to the nearest vial size) twice weekly, three times weekly, or every other day for 6 months  >12 year-old: 20 to 40 IU of KOVALTRY per kg of body weight (rounded to the nearest vial size) two or three times per week for 6 months	15 to 50 IU (minimum 250 IU) of KOVALTRY per kg body weight [rounded to the nearest vial size]) at least 1 day per week.  Alternatively, prophylaxis can be started directly with a once-a-week schedule minimum dose of 250 IU for PUPs/MTPs of any weight.  The starting dose may be tailored to the participant's weight or demonstrated bleeding tendency.  Treatment is continued until 50 ED is achieved.
Route of Administration	IV infusion	IV infusion	IV infusion

Arm Name	Part A		Part B
	Child (Age <12 years)	Adolescent/Adult (Ages ≥12 to 65 years)	Child (Age <6 years)
Packaging and Labeling (identical for all arms)	Study intervention will be provided in vials packaged together with a container of the appropriate amount of sterile water for infusion for reconstitution. For KOVALTRY, the volume of diluent is 2.5 mL for all vial sizes. The vials will also be supplied with an infusion set composed of 1 syringe containing the diluent and 1 butterfly needle to facilitate infusion. Instructions for reconstitution are supplied in each kit. The kits will be labeled as required by the Chinese Regulatory Authority. Instructions on storage and transport of the drugs provided for home administration will be provided in training given at the Baseline visit.	Study intervention will be provided in vials packaged together with a container of the appropriate amount of sterile water for infusion for reconstitution. For KOVALTRY, the volume of diluent is 2.5 mL for all vial sizes. The vials will also be supplied with an infusion set composed of 1 syringe containing the diluent and 1 butterfly needle to facilitate infusion. Instructions for reconstitution are supplied in each kit. The kits will be labeled as required by the Chinese Regulatory Authority. Instructions on storage and transport of the drugs provided for home administration will be provided in training given at the Baseline visit.	Study intervention will be provided in vials packaged together with a container of the appropriate amount of sterile water for infusion for reconstitution. For KOVALTRY, the volume of diluent is 2.5 mL for all vial sizes. The vials will also be supplied with an infusion set composed of 1 syringe containing the diluent and 1 butterfly needle to facilitate infusion. Instructions for reconstitution are supplied in each kit. The kits will be labeled as required by the Chinese Regulatory Authority. Instructions on storage and transport of the drugs provided for home administration will be provided in training given at the Baseline visit.
Current/Former Name(s) or Alias(es)	Commercial name: KOVALTRY (BAY 81-8973)	Commercial name: KOVALTRY (BAY 81-8973)	Commercial name: KOVALTRY (BAY 81-8973)

KOVALTRY will also be used for treatment of bleeding events and with surgical procedures (see Section 10.4) and optional ITI (see Section 10.5).

For optional ITI treatment with Kovaltry, ITI will be provided at a dose of up to 200 IU/kg daily for up to a maximum of 18 months or until failure (see Section 10.5 for additional information).

## 6.2 Preparation/Handling/Storage/Accountability

The instructions for reconstitution using a vial adaptor will be provided to the participant and/or his parent/caregiver at the start of the study, and study site staff will instruct all participants and/or their caregivers on how to reconstitute and administer KOVALTRY.

The participants and/or their caregivers will be instructed to administer reconstituted KOVALTRY as soon as possible, and no longer than 3 hours after reconstitution, according to the individual participant's dosing schedule.

KOVALTRY must be stored under refrigeration (2°C to 8°C, do not freeze). Participants and parents/caregivers will be provided with detailed instructions for proper storage of the study intervention.

KOVALTRY must be stored at the investigational site in accordance with Good Clinical Practice (GCP) and Good Manufacturing Practice (GMP) requirements and the instructions given by the clinical supplies department of the Sponsor or its affiliates.

Special study site storage conditions and a complete record of batch numbers and expiry dates can be found in the Sponsor's study file; the site-relevant elements of this information will be available in the investigator site file. On the day of receipt, the responsible site personnel will confirm receipt of study intervention via IxRS.

1. The investigator or designee must confirm appropriate temperature conditions have been maintained during transit for all study intervention received, and any discrepancies are reported and resolved before use of the study intervention.
2. Only participants enrolled in the study will receive study intervention and only authorized site staff may supply or administer study intervention. All study intervention must be stored in a secure, environmentally controlled, and monitored (manual or automated) area in accordance with the labeled storage conditions with access limited to the investigator and authorized site staff. Participants and/or their parents/caregivers will be instructed on proper storage at home.
3. The personnel will use the study intervention only within the framework of this clinical study and in accordance with this protocol.
4. The authorized site staff is responsible for study accountability, reconciliation, and record maintenance. Receipt, distribution, return and destruction (if any) of the study intervention must be properly documented according to the Sponsor's agreed and specified procedures.
5. Further guidance and information for the final disposition of unused study interventions are provided separately.

### **6.3 Measures to Minimize Bias: Randomization and Blinding**

Not applicable. The study arms are based only on age and/or treatment status (PTPs and PUPs/MTPs). This is an open label study, and no blinding or randomization will be used.

### **6.4 Study Intervention Compliance**

Participant compliance with study intervention/treatment will be assessed at each visit.

Used and unused vials of study medication will be returned to the clinic at every site visit for accounting. Any discrepancies between actual and expected number of returned vials must be discussed with the participant at the time of the visit, and any explanation must be documented in the source records.

When participants are dosed at the site (at Baseline and the indicated study visits in Section 1.3.1 [Part A] or Section 1.3.2 [Part B] as per their individual participant's regimen), they will receive study medication according to the standard of the institution. The date and time of each dose administered in the clinic will be recorded in the source documents and recorded in the case report form (CRF).

The majority of dosing will be done at home, by the participant or his parent/caregiver, in accordance with the written instructions and demonstration provided by study center staff at the Baseline visit. Instruction on reconstituting KOVALTRY and other aspects of IV administration will be provided in detail.

In Part A, KOVALTRY will be dispensed on a monthly basis (in accordance with the individual drug dispensing schedule every 28 [ $\pm 7$ ] days) at the study center and will not be linked to the scheduled study visit schedule (see Section 1.3.1). In Part B, drug dispensing will be done in accordance with the individual drug dispensing schedule; additional drug dispensing visits might be performed between Visit 6 and the Final visit in order to ensure study participants have sufficient study drug to cover the period between the scheduled study visits (see Section 1.3.2).

The electronic patient diary (EPD) will be the source document that will be used to assess the participant's compliance with the treatment schedule/dose and to reconcile study medication inventory. The EPD will be used to record date and time of self-administration of study intervention for prophylaxis, as well as every bleeding episode with details of the bleeding and administered intervention. Data on the EPD will be transmitted on a regular basis.

The EPD will be reviewed at visits and at regular contacts with the participant and/or his parent/caregiver during the study.

## 6.5 Concomitant Therapy

Any medication or vaccine (including over-the-counter or prescription medicines, vitamins, and/or herbal supplements) that the participant is receiving at the time of enrollment or receives during the study must be recorded in the CRF along with:

- Reason for use
- Dates of administration including start and end dates
- Dosage information including dose and frequency

The Study Medical Expert should be contacted if there are any questions regarding concomitant or prior therapy.

Bleeding episodes that occur during the screening period (Screening visit until Visit 2) will be treated with the participant's previous FVIII product.

All medications and blood products required by the participant after the informed consent is signed, including FVIII products other than study intervention, will be listed in the appropriate eCRF page. All concurrent prescription and non-prescription medications including over-the-counter and alternative preparations (including herbal remedies, vitamins, and health food supplements), antibiotics, and pain medications being administered starting at least 3 months, and FVIII and bispecific activated FVIII mimetic products at least 12 months prior to study enrollment, will be recorded in the CRF at screening and throughout the treatment period and follow-up call.

The participant should not be taking any other investigational drug or any other FVIII treatment (except in emergencies) while receiving treatment with KOVALTRY.

Pre-medications to tolerate treatment with KOVALTRY are not allowed. Use of topical anesthetics prior to venipuncture is permitted.

Medications which cause a bleeding diathesis (for example, Aspirin® or any acetylsalicylic acid) should be avoided in individuals with hemophilia, except as specifically prescribed by a treating physician. Low dose aspirin should not be discontinued in participants who have been identified to be at risk for cardiovascular events. The decision to prescribe non-steroidal anti-inflammatory drugs, cyclooxygenase-2 (COX-2) inhibitors, or brief courses of corticosteroids to treat pain or acute synovitis is at the discretion of the treating physician.

Inhaled or topical steroid medications (as for the treatment of asthma or eczema) are allowed. Brief courses of prednisone/methylprednisolone (<14 days) for treatment of disorders such as synovitis, asthma, etc. are at the discretion of the treating physician. For any participant requiring longer courses of corticosteroids or use of other immunomodulatory treatment, the investigator should notify the Sponsor.

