- j Study intervention will be administered throughout the study in accordance with the assigned prophylaxis regimen. Drug dispensing will be done in accordance with the individual drug dispensing schedule. Additional drug dispensing visits could be performed between Visit 6 and the Final visit in order to ensure study participants have sufficient study drug to cover the period between the scheduled study visits.
- k The EPD may be given to the parent/caregiver to take home at any time between the Screening and Baseline visits, but no entries should be made before the first infusion of study drug at the Baseline Visit.
- l Blood samples for FVIII level will be taken pre-infusion and at 15 to 30 minutes after end of infusion to calculate recovery at the Baseline visit and Visits 6 and 8 (Final visit). Infusion doses for recovery measurements must be given in hospital and directly reported in RAVE. The bioanalysis will be done at a local laboratory.
- m For PUPs who do not start treatment with study drug at the Baseline, recovery evaluation should be done at the study visit when prophylaxis is started.
- n Standard laboratory assessments include hematology and clinical chemistry. Guidance for blood draws in participants ≤10 kg is provided in Section 10.2.
- o Inhibitor will be evaluated at every visit after the start of treatment with study drug for MTPs as well as for PUPs. FVIII level and presence of FVIII inhibitor should be measured at least 48 hours after the last dose of study drug. The first positive inhibitor test after start of treatment with study drug must be confirmed by analysis of a second sample and by analysis of FVIII level recovery within 2 weeks of the investigator's notification.
- p Study center staff will call the parents/caregivers of participants approximately every 2 weeks between Baseline and Visit 8 (Final visit) and approximately 2 weeks after the last visit to verify proper completion of the participant diary and to review any new AEs and changes in concomitant medication since the last study visit.

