**Type of Participant and Disease Characteristics**

2. Chinese participants with severe hemophilia A (defined as FVIII:C <1% with one-stage clotting assay documented at the time of screening). If screening results show FVIII:C as equal to or higher than 1%, then severe hemophilia A may be confirmed by documented historical evidence from a (certified) clinical laboratory demonstrating FVIII:C <1% as determined by a one-stage clotting assay.
3. PUPs must have no previous exposure to any FVIII product.  
MTPs must have no more than 1 ED with any purified FVIII concentrate or 3 exposures with FFP or cryoprecipitate.
4. MTPs have no current evidence of inhibitor antibody as measured by the Nijmegen-modified Bethesda assay (<0.6 BU/mL) in 2 consecutive samples and must have absence of clinical signs or symptoms of decreased response to FVIII administration. Testing for the 2 negative samples must be performed by the local laboratory at least 1 week but not more than 2 weeks apart. Participants may not receive FVIII product within 72 hours prior to the collection of samples for inhibitor testing.

5. PUPs and MTPs must observe a 6-month washout period if they have received subcutaneous factor substitution therapy (emicizumab).
6. PUPs may be included if they will receive their first FVIII dose with KOVALTRY for treatment of first bleeds and agree to start prophylaxis as part of their care.  
MTPs may be included if they agree to start prophylaxis as part of their care.

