## 7.2 Study Visits - Part B (PUPs/MTPs)

Part B consists of a screening period followed by at least 50 ED per participant.

For MTPs, the Screening visit should only take place after a washout period of at least 72 hours following previous treatment with any FVIII replacement product.

The treatment period will last until 50 ED have been accumulated. The duration will vary and is dependent upon the frequency of prophylactic infusion and the number of bleeding events.

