### 7.2.2 Visit 2/Baseline (No Later Than 4 Weeks From Visit 1)

For MTPs, this visit will include the first administration of study drug.

For PUPs, the first dose of KOVALTRY may be for treatment of a bleed. First treatment should not occur during high risk situations, surgery, or bleeds requiring prolonged or intensive treatment (see Section 6.6.2).

The following activities will be performed:

- Inclusion/exclusion criteria verification, i.e., confirmation of eligibility including check of laboratory test results.  
Note: MTPs must be inhibitor negative as evaluated via local laboratory testing at the Screening visit. A confirmatory inhibitor test must be taken at least 1 week but not more than 2 weeks after the Screening visit. Results from local laboratory testing must be negative ( $<0.6$  BU/mL) prior to administration of study intervention.
- Height/length and weight
- Vital signs (including systolic and diastolic blood pressure, heart rate, and body temperature); blood pressure may be deferred if the appropriate cuff size or equipment is not available (see Section 8.2 for details)
- Concomitant medication review
- Blood sampling before administration of study drug intervention
  - FVIII inhibitor assessment (Section 8.10; not required for PUPs but required for MTPs)

- In-hospital administration of the first dose of study drug (for MTPs and PUPs who are starting treatment at baseline).  
Note: First exposure to study drug may be either for treatment of an uncomplicated bleed or for start of prophylaxis. Inhibitor testing is mandatory every 3 to 5 ED until 20 ED are accumulated (see Section 6.6.2).
- Blood sampling after administration of study intervention (Section 7.3.2):
  - Incremental recovery (15 to 30 minutes post infusion) only for participants who start prophylaxis at Baseline; for PUPs who do not start prophylaxis at baseline, recovery should be done when prophylaxis is started
  - AE review
  - Study drug dispensation for home infusions in accordance with the IxRS drug dispensing schedule
  - Diary training review; participants/caregivers will be instructed to complete the EPD as required (see Section 7.3.1) beginning at Baseline through the end of the study (see Section 4.4)
  - Instruction on the prophylaxis regimen to be administered to the participant
  - Begin regular biweekly contact between the participant's parent/caregiver and the site to check EPD documentation and AE review until the End of Study/Early Termination

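### The Protocol 6.5 rule for bleeds in screening has no Part B exception: it takes an MTP already at the exposure limit over it, and it cannot be applied to a PUP

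*Protocol*

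**What the plan says.** Protocol 6.5 covers concomitant therapy for the whole study and states: "Bleeding episodes that occur during the screening period (Screening visit until Visit 2) will be treated with the participant's previous FVIII product". Neither that section nor the Part B sections (6.6.2, 7.2) make an exception for Part B.

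The Part B entry rules in 5.1.2 are tight on prior exposure. Criterion 3 states "PUPs must have no previous exposure to any FVIII product" and "MTPs must have no more than 1 ED with any purified FVIII concentrate or 3 exposures with FFP or cryoprecipitate". Criterion 6 adds: "PUPs may be included if they will receive their first FVIII dose with KOVALTRY for treatment of first bleeds".

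On timing, 7.2 states: "For MTPs, the Screening visit should only take place after a washout period of at least 72 hours". Section 7.2.2 states: "A confirmatory inhibitor test must be taken at least 1 week but not more than 2 weeks after the Screening visit". MTPs may not start KOVALTRY until the local inhibitor result is negative (1.3.2, note h). Visit 2 may fall up to 4 weeks after Visit 1.

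Eligibility is verified again at Visit 2 (7.2.2) and waivers are barred (Sections 5 and 7). Section 5.4 adds: "Individuals who do not meet the criteria for participation in this study (screen failure) cannot be rescreened".

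PUPs have no inhibitor test before study treatment (1.3.2, note h; 8.10.2). SAP 6.4.2 treats an inhibitor as treatment-emergent if it develops after the first study drug application.

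**The concern.** The 6.5 sentence suits a Part A participant, who has been on a FVIII product for at least 50 or 150 EDs. In Part B it meets children whose eligibility depends on having had almost no FVIII. For an MTP at the limit, a site that follows 6.5 breaks criterion 3. For a PUP there is no previous product, so the sentence gives the site no instruction.

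Part B plans about 6 evaluable children from about 10 screened, so each child is about 17% of the sample. Inhibitor development is a key safety outcome, and Protocol 6.6.2 itself says the timing of first FVIII exposures may matter for tolerance. If a PUP were given another FVIII product in screening, an inhibitor caused by it could first be found at Visit 3 (about 5 ED) and be counted as arising on KOVALTRY.

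**Working it through.** **1. The plan's own figure.** Protocol 9.2.2 gives at least a 92% chance of seeing one or more inhibitors among 6 children at a true rate of 35%. Check: 1 − 0.65^6 = 1 − 0.0754 = 92.5%. It reproduces. The statement of more than 90% reassurance when no inhibitor is seen rests on the same number.

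**2. Exposure count against criterion 3.** Inputs: limits of 1 concentrate ED or 3 FFP/cryoprecipitate exposures; one treatment day in screening. The washout of at least 72 hours before Screening means that a screening dose cannot share an exposure day with an earlier one.

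| Status at Screening | One more day of | Count | Within limit? |
|---|---|---|---|
| MTP, 1 concentrate ED | concentrate | 1 + 1 = 2 | No (limit 1) |
| MTP, 3 FFP/cryoprecipitate | FFP/cryoprecipitate | 3 + 1 = 4 | No (limit 3) |
| MTP, 1 or 2 FFP/cryoprecipitate | FFP/cryoprecipitate | 2 or 3 | Yes |
| MTP, FFP/cryoprecipitate only | concentrate | 0 + 1 = 1 | Yes |
| PUP | no previous product | – | 6.5 cannot be applied |

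A PUP who received one day of another concentrate would have 0 + 1 = 1 ED. That ends PUP status and falls within the MTP exposure limit. However, an MTP needs two negative inhibitor samples (criterion 4), which a PUP does not have, and no text provides for reclassification.

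**3. Can the window be avoided?** Not by an MTP: the second inhibitor sample makes screening at least 1 week long, and study drug waits for the result. Criterion 3 does not say when exposures are counted. If at Visit 2, the child in row 1 or 2 is excluded without rescreening. If only at Screening, he enters above the limit.

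**4. How often?** The documents give no bleed rate before prophylaxis. Assume r treated bleeds a year, Poisson, over d days: P(at least one) = 1 − exp(−r·d/365.25).

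| r (assumed) | 7 days | 28 days |
|---|---|---|
| 1 | 1.9% | 7.4% |
| 4 | 7.4% | 26.4% |
| 12 | 20.5% | 60.1% |

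The upper rates fit these children poorly. Under the same model, the chance of at most one treated bleed in a whole prior year is e^(−r)(1 + r): 74% at r = 1, 9% at r = 4 and 0.008% at r = 12. These are probabilities of a screening bleed, not of a breach; a breach also needs the child to be at his limit.

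**5. Effect of losing one child.** With 5 evaluable children: 1 − 0.65^5 = 1 − 0.1160 = 88.4%. Both the 92% statement and the more-than-90% statement then fail.

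**The case against.** The case against narrows the point considerably, and most of it stands.

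- A reader might infer that 6.5 sends a PUP to another FVIII product. It does not: he has no previous product, so the sentence is inoperative. Criterion 6, 6.6.2 and 7.2.2 all allow his first KOVALTRY dose to be for a bleed, and Visit 2 could be brought forward. What is left is a bleed before eligibility is confirmed.
- A reader might infer that every MTP treated in screening breaks the limit. Only rows 1 and 2 of the exposure table do.
- A reader might infer that study exposure days are miscounted or that a planned subgroup is corrupted. The SAP counts days with a study drug infusion (5.1, per protocol set), Part B runs to 50 ED of study intervention (Protocol 7.2.8), and no Part B summary is split by PUP/MTP.
- A reader might infer that non-study FVIII given after Visit 2 is never caught before the first study dose. The 6.5 rule stops at Visit 2, 7.2.1 bars study drug unless all criteria are met, and the two-weekly calls review concomitant medication (1.3.2, note p). There is no scheduled recheck, but 6.5 does not cause such exposure.
- The Part B primary endpoint is untouched, because bleeds before prophylaxis are not counted (SAP 4.5). The study is descriptive, and a screen failure may be replaced. MTPs enter with some prior exposure by definition, so attribution of an inhibitor to KOVALTRY is already imperfect for them.

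None of this removes the conflict for an MTP at his limit. There, one stated instruction defeats another, with no waiver and no rescreening.

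**Conclusion.** The point holds in limited form. Following 6.5 puts an MTP already at 1 concentrate ED over the criterion 3 limit. The same is true of an MTP at 3 FFP/cryoprecipitate exposures if that is the product repeated. For a PUP, 6.5 leaves a bleed before confirmed eligibility uncovered. The inhibitor concern is smaller and conditional: it arises only if a PUP does receive another FVIII product in screening, and then the missing pre-treatment test and the treatment-emergent definition together assign a later inhibitor to KOVALTRY.

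The contradiction itself rests on no assumption. Its frequency does: the bleed rates are assumed, and 4 weeks is the longest screening allowed, with the second MTP sample due at 1 to 2 weeks. The fall from 92% to 88% applies only if one evaluable child is lost and not replaced.

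**What to change.** - Reconcile 6.5 with 5.1.2 (criteria 3, 4 and 6), 5.4, 7.2.2 and note h of the Part B schedule, so that the text covers an MTP at his limit and a PUP who bleed before the first KOVALTRY dose. Which treatment applies is the sponsor's clinical decision.
- State that FVIII, FFP and cryoprecipitate exposures are recounted immediately before the first KOVALTRY dose, and that PUP/MTP status is set from that count. Say also whether a reclassified PUP then falls under the criterion 4 inhibitor tests.
- In the SAP, flag in the inhibitor listing any Part B child given non-study FVIII after Visit 1, and present the inhibitor proportion with and without such children.

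The cost is a short amendment, one check on data that 6.5 already requires to be recorded, and one extra summary. The downside is that a child may be reclassified or flagged; with about 6 children, leaving one out removes about 17% of the denominator, so both proportions should be shown.
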